7. RATIONALE AND BACKGROUND

Multiple myeloma (MM) is a hematological malignancy originating in plasma cells in the bone marrow.^{1,2} Healthy plasma cells secrete antibodies, also known as immunoglobulins, to fight infection and act as the humoral line of defense.^{1,2} Plasma cells that have become cancerous (i.e., myeloma cells) proliferate and displace normal cell production in bone marrow, among other effects on the immune system. As a consequence, the general production of antibodies is impaired, decreasing the body's supply of antibodies.³ MM is characterized by an increase in non-functional monoclonal proteins (M proteins), a decrease in blood count, renal failure, end-organ damage, susceptibility to infections, and bone weakness.^{1–3} The incidence of MM was 7.4 per 100,000 people in the United States (US) from 2016-2020, while the 5-year relative survival from 2013 to 2019 was 59%.⁴ MM is the second most prevalent hematological malignancy and accounted for approximately 1.8% of all new cancer cases in 2023.^{5,6}

Many therapies for MM exist, and clinical advances continue to change the treatment landscape. The advent of therapies, such as proteasome inhibitors (PIs), immunomodulatory drugs (IMiDs), and monoclonal antibodies (mAbs), has increased the overall survival of MM patients. ^{7–9} Despite numerous advances in the available therapies for MM, most patients with MM will either relapse (fail to respond to treatment) or become refractory (have their treatment fail). ¹⁰ These patients are collectively referred to as having relapsed or refractory multiple myeloma (RRMM). Given relapse to later lines confers progressively worse outcomes including shorter survival time, there is a need to investigate alternative treatment options in this setting. ^{9,10}

Recent improvements in treatment for patients with RRMM included advances in B-based treatments targeting B-cell maturation antigen (BCMA), which is primarily present in malignant plasma cells. BCMA is expressed in B-cells and regulates their maturation into plasma cells. BCMA bispecific antibodies (BsAb) target and bind BCMA-expressing plasma cells and the CD3 receptor on T-cells, activating cytotoxic activities of the T cell. Elranatamab is approved in the US for patients who have received at least four lines of therapy, including a PI, an immunomodulatory agent, and an anti-CD38 mAbs. 12

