Teclistamab, another BCMA BsAb, was approved in October 2022, based on results from the MajesTEC-1 trials; the ORR was 63.0%, and common adverse events included infections (76.4%), cytokine release syndrome (72.1%), anemia (52.1%), and neutropenia (70.9%). Elranatamab was approved in August of 2023, based on the results from the MagnetisMM-3 trial, a phase 2 trial aimed at assessing the efficacy of elranatamab monotherapy. The ORR was 61.0%, and common adverse events included infections (69.9%), cytokine release syndrome (57.7%), anemia (48.8%), and neutropenia (48.8%). While some published studies have assessed the real-world utilization of other BCMA BsABs such as teclistamab, the real-world usage of elranatamab has not been characterized. This study aims to describe the uptake and use of elranatamab subsequent to the August 2023 Food and Drug Administration (FDA) approval.

This noninterventional study is designated as a PASS and is conducted voluntarily by Pfizer.

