Exploratory Obj 1	Other infectious hepatitis ²	Medical claim with an ICD-10 code in the inpatient, non-IP or pharmacy setting for infectious hepatitis (other than hepatitis B or C) (dichotomous)	Index date to end of follow-up, where follow-up will be based on last dose of elranatamab or teclistamab (e.g., 14 days after last recorded dose or 90 days after last recorded dose).
Exploratory Obj 1	Helicobacter pylori ²	Medical claim with an ICD-10 code in the inpatient, non-IP or pharmacy setting for helicobacter pylori (dichotomous)	Index date to end of follow-up, where follow-up will be based on last dose of elranatamab or teclistamab (e.g., 14 days after last recorded dose or 90 days after last recorded dose).

Exploratory Obj 1	Candida esophagitis ²	Medical claim with an ICD-10 code in the inpatient, non-IP or pharmacy setting for candida esophagitis (dichotomous)	Index date to end of follow-up, where follow-up will be based on last dose of elranatamab or teclistamab (e.g., 14 days after last recorded dose or 90 days after last recorded dose).				
Exploratory Obj 1	Urinary tract infection ²	Medical claim with an ICD-10 code in the inpatient, non-IP or pharmacy setting for a urinary tract infection (dichotomous)	Index date to end of follow-up, where follow-up will be based on last dose of elranatamab or teclistamab (e.g., 14 days after last recorded dose or 90 days after last recorded dose).				
Exploratory Obj 1	Time to infection onset	Time in days from index date to first infection for the following infections:	Index date until censor				
Effectiveness	Effectiveness						
Exploratory Obj 2	os	Time (in months) from index date until date of death (continuous)	Index date until censor				
Exploratory Obj 2	TTNT/D	Time (in months) from index date until the date of the next treatment (CAR-T, BsABs, bendamustine or belantamab) or death (continuous)	Index date until censor				

- 1. Variable will be measured as incident and prevalent. Incident cases have 30-day washout period applied
- 2. Variable will be measured as incident and prevalent. Incident cases have 60-day washout period applied
- 3. Variable will be measured as incident and prevalent. Incident cases have 14-day washout period applied

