9.7.6. Tolerability

The prevalence and incidence for each adverse event (Table 3) will be estimated. All prevalence and incidence estimates will be reported as a percent with corresponding 95% CIs.

Prevalance =
$$(\frac{No.\ of\ patients\ with\ an\ event}{Total\ number\ of\ patients\ in\ the\ cohort})\ x\ 100$$

For the incidence analysis, only patients who did not have the event prior to their index date will be included. The length of the washout is dependent on the outcome (see Table 3).

$$Incidence = \left(\frac{\text{No. of patients with an event that did not have an event in baseline}}{\text{Total number of patients in the cohort}}\right) x \ 100$$

PFIZER CONFIDENTIAL

Patients will be assessed over two time periods: from the index date until 14 days or 90 days after their last administration of the index medication.

Additionally, the time to infection onset will be assessed using unadjusted Kaplan-Meier methods. The median time to event in days will be reported along with the IQR. The 95% CIs for the median time to event will be calculated using log-log transformation.

Patients will be censored at the earliest of death, next treatment (CAR-T, BsABs, bendamustine or belantamab), the end of part A or B continuous closed-claim coverage, or the end of data.

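### Time to infection onset is estimated by Kaplan-Meier with death censored, so the reported median and upper quartile describe a population without death and can only be as early as, or earlier than, the cohort's own times

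*Protocol*

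**What the plan says.** Protocol section 9.7.6 (Tolerability) fixes three things for this outcome.

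- The estimator: "the time to infection onset will be assessed using unadjusted Kaplan-Meier methods".
- The summaries: "The median time to event in days will be reported along with the IQR", with log-log confidence intervals for the median.
- The censoring rule, in the last paragraph of the section: "Patients will be censored at the earliest of death, next treatment (CAR-T, BsABs, bendamustine or belantamab), the end of part A or B" coverage, or the end of data.

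Table 3 in section 9.3 defines the outcome as "Time in days from index date to first infection for the following infections". Death is not part of the event. By contrast, time to discontinuation (9.7.5) and TTNT/D (9.7.7) count death as an event.

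The protocol names no competing-risk method, and section 9.9 does not list the matter as a limitation. Section 9.7 allows the SAP to modify the plan, but the choices here are already explicit, and section 9.8 says that the protocol will be followed strictly.

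**The concern.** Censoring assumes that a patient who leaves observation would have gone on to have infections at the same rate as those who remain. That is reasonable for the end of data. It has no meaning for a patient who has died, who cannot have a first infection.

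Kaplan-Meier with death censored therefore estimates how fast infections would occur if nobody died. The protocol does not state that as its target; Exploratory Objective 1 is to describe real-world safety. Its own background says of this disease: "Given relapse to later lines confers progressively worse outcomes including shorter survival time". It also names susceptibility to infection as a feature of myeloma, so independence of death and infection risk is doubtful as well.

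At stake are the median and IQR of infection onset. A reader would take them as the times by which a quarter, half and three quarters of the treated cohort had an infection, and they are not those times.

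**Working it through.** **Nothing to reproduce.** The protocol states no figure for time to infection and no mortality rate for this cohort. The direction can be proved; the size can only be illustrated.

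**Direction.** Let λ be the infection hazard and μ the hazard of infection-free death. Kaplan-Meier with death censored targets 1 − exp(−∫λ). The cohort's cumulative incidence is ∫ λ(s)·exp(−∫₀ˢ(λ+μ)) ds. The second is never larger than the first and is strictly smaller once infections occur after an infection-free death. Kaplan-Meier quantiles are thus never later than the cohort's.

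**Inputs for the illustration**

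- Infection: 69.9%, the phase 2 elranatamab frequency in section 7. Its use as a net 12-month risk of any infection is an assumption.
- Infection-free death: μ = 0.01, 0.02, 0.03 or 0.05 per month. Assumed.
- Constant hazards. Assumed.
- No deaths before day d = 30. Eligibility requires 30 days of enrolment after index (9.2.1), so this holds if death ends enrolment.
- 1 month = 30.4375 days (9.7.5).

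**Kaplan-Meier target.** λ = −ln(1 − 0.699)/12 = 0.1001 per month. The time to proportion p is −ln(1 − p)/λ:

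- median: 0.6931/0.1001 = 6.93 months = 210.9 days
- upper quartile: 1.3863/0.1001 = 13.86 months = 421.7 days

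**Cumulative incidence.** With S = exp(−λd) = 0.906, for t > d:

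F(t) = 1 − S + S·[λ/(λ+μ)]·[1 − exp(−(λ+μ)(t − d))], with plateau 1 − S + S·λ/(λ+μ).

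Example, μ = 0.05: the plateau is 0.094 + 0.906 × 0.667 = 0.698, so 75% is never reached. For the median, (0.5 − 0.0939)/0.6042 = 0.672; −ln(1 − 0.672)/0.1501 = 7.43 months = 226 days; adding 30 gives 256 days.

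| μ per month | Lower quartile (days) | Median (days) | Upper quartile (days) | Plateau |
|---|---|---|---|---|
| Kaplan-Meier, death censored | 87.5 | 210.9 | 421.7 | – |
| 0.01 | 88.1 | 217.8 | 470.3 | 91.8% |
| 0.02 | 88.7 | 225.6 | 545.0 | 84.9% |
| 0.03 | 89.3 | 234.5 | 693.2 | 79.1% |
| 0.05 | 90.6 | 256.2 | not reached | 69.8% |

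The median is about 7, 15, 24 and 45 days too early. The lower quartile barely moves.

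**Sensitivity**

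- Deaths counted from day 0: the median shifts grow to 10, 21, 35 and 70 days, and the upper quartile becomes 482, 584, 862 days or not reached.
- Net 12-month risk of 50%, no deaths before day 30: Kaplan-Meier gives a median of 365 and an upper quartile of 730 days. The cumulative incidence gives a median of 391 to 625 days. Its upper quartile is 922 days at the lowest hazard, 1,831 at the next, and not reached at the other two. The longest possible follow-up, 14 August 2023 to 31 December 2025, is 870 days, so only Kaplan-Meier could report one.
- Net 12-month risk of 10% (a single uncommon infection): even the Kaplan-Meier lower quartile is 997 days, beyond 870. No quartile would be expected under either method.

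**Finite-sample check.** Simulation used n = 133 (the count in section 9.5), an infection median of 6 months, deaths from day 0, and administrative censoring uniform over 9 to 28 months. Kaplan-Meier reported an upper quartile in every replicate, typically 361 to 365 days. The competing-risk estimate did not reach 75% in 97%, 59% and 23% of replicates for assumed median OS of 12, 18 and 24 months.

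**The case against.** The strongest reply is that this matters little. Safety is an exploratory objective, and time to infection is one added sentence. The lower quartile hardly moves, and at the lower assumed hazards the median moves by one or two weeks. This stands, and it limits the weight of the point.

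A reader might go further and infer that the study will overstate how frequent infections are. The protocol does not support that. Infection frequencies are reported as the prevalence and incidence percentages of 9.7.6. These are crude proportions in which patients who die stay in the denominator, so they do not carry this bias. Nor does 9.7.6 plan a Kaplan-Meier infection percentage at 12 months, so a gap in percentage points at that time would concern a statistic that is not specified.

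The size is also open to challenge, rightly. The mortality is assumed over a fivefold range. The 69.9% is a trial adverse-event frequency quoted without a time horizon. The list of infections attached to the outcome in Table 3 is not legible in the text available. If onset is reported by individual infection, 69.9% does not apply and the effect on the reported quantiles is small.

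One could defend Kaplan-Meier as a deliberate estimate of infection onset in the absence of death. That needs the target to be stated and death to be independent of infection risk; the protocol says neither. None of these replies changes the direction of the error or removes the upper-quartile problem for any infection or for common ones.

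**Conclusion.** The point holds for the median and IQR of time to infection onset and for nothing else in 9.7.6. The direction is certain: the reported quantiles are equal to or earlier than the cohort's. The size cannot be determined from the protocol. Under the assumed any-infection scenario with no deaths before day 30, the median is about 7 to 45 days early. The upper quartile is about 49 days early (470 − 422) at the lowest hazard and is not reached at the highest, where Kaplan-Meier still reports 422 days. These figures rest on constant hazards, a 69.9% net 12-month risk and assumed death hazards of 0.01 to 0.05 per month. This is a cheap improvement to an exploratory descriptive summary. It does not threaten the primary objectives.

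**What to change.** In section 9.7.6, replace the Kaplan-Meier sentence for infection onset. Estimate the Aalen-Johansen cumulative incidence of first infection with death before infection as a competing event. Report it with 95% confidence intervals at fixed, pre-stated times, and take the 25%, 50% and 75% times from that curve where reached.

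Keep censoring at the end of Part A or B coverage and at the end of data. Handle next treatment explicitly, because the present sentence also censors there:

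- if the target is infection before a switch, make next treatment a second competing event;
- if the target is infection regardless of a switch, do not end follow-up at next treatment.

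The cost is a short text change and a standard procedure, with no new data; the final analysis is planned for 27 February 2026. The downside is that some quantiles will be later, or will have to be reported as not reached.

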9.7.7. Overall Survival and Time to Next Treatment

OS and TTNT/D will be assessed using unadjusted Kaplan-Meier methods. The median time to event in months will be reported along with the IQR. The 95% CIs for the median time to event will be calculated using log-log transformation. Results will be depicted graphically by Kaplan-Meier curves, and the percentage of patients who reached the outcome and censored patients will also be reported.

OS will be assessed as the time in months from index date to date of death. TTNT/D will be assessed as the time in months from index date until switch a new treatment or death. Patients will be censored at the earliest of death, next treatment (CAR-T, BsAbs, bendamustine or belantamab), the end of continuous closed-claim coverage, or the end of data. Patients without an event will be censored at the earliest of the end of continuous closed-claim coverage or end of data.

9.8. Quality Control

Clarify Health will code measures for cohort identification, outcomes, and other variables of interest based on codes and algorithms described in this protocol. This protocol will be strictly followed when conducting the analysis of this study. All cohorts developed, statistical analyses implemented, and tables completed will undergo quality control review by at least one additional analyst or scientist under the supervision of the Study Lead. The Study Lead will review all results tables and other final deliverables to confirm accuracy, logical flow, and appropriate format.

9.9. Limitations of the Research Methods

While claims databases provide a wealth of comprehensive information to assess patients' demographic and clinical characteristics, a few limitations arise when using such databases. For instance, there may be misclassification of patient records due to provider coding practices (e.g., using a diagnosis code as a rule-out criterion) or incorrect coding (e.g., data entry errors). As such, the presence of a diagnosis code may not always accurately reflect the presence of disease for an individual patient. Such errors could affect patient eligibility and all variables used to assess treatment characteristics, HCRU, etc. Another potential issue that arises when using any database is generalizability. Oftentimes, the demographic makeup of the dataset is dependent on the providers

that supply the information; if a dataset is heavily receiving data from one region of the US, then that might affect overall generalizability.

The proposed analysis, consistent with claims analyses more generally, is subject to certain inherent limitations. The underlying Medicare data reflect a publicly-insured, elderly and/or disabled patient population and may not be representative of other payer populations. Although we plan to include individuals in the dataset aged younger than 65+ qualifying for Medicare due to a disability or ESRD status, the overall sample population will be older and have a higher disease burden than an overall US population would be.

Clinical events of interest defined by diagnosis codes may not capture the occurrence or intensity of the disease. Certain conditions, such as hematological toxicities, are often defined via specific cutoffs for certain lab values, which are not often provided in a claims data source. Therefore, ICD codes are used instead. Without lab values, the severity of the disease/grade cannot be determined. Therefore, patients whose adverse events were not as severe in grade may not be captured. Claims data do not contain variables used to assess standard oncology endpoints. Claims databases do not often detail clinical contexts, such as physician notes, imaging results, or laboratory findings. Common oncology endpoints such as real-world progression-free survival, real-world objective response rate, and reasons for discontinuation are typically defined using variables abstracted from patient charts that are not available in a claims dataset. Similarly, any treatments or drug utilization (such as over-the-counter purchasing of medications directly by patients) not directly reimbursed by the Medicare program will not be available for review.

The recency of elranatamab and teclistamab approval is important for interpreting results. The expected sample size is low, potentially resulting in uncertain estimates, as evidenced by wide confidence intervals. Very few eligibility criteria will be applied, which may allow patients with other malignancies or other conditions that are often excluded in a real-world study to enter. Additionally, the patients who have received elranatamab or teclistamab soon after approval may have more severe or advanced disease. Due to the recency of approval, the generalizability of outcomes may be limited to a brief period following initiation.

9.10. Other Aspects

Not applicable

10. PROTECTION OF HUMAN PARTICIPANTS

10.1. Patient Information

This study involves secondary data that exist in deidentified/anonymized structured format and contain no patient personal information. Clarify has been granted an IRB exemption for observational, retrospective research using the 100% Medicare FFS data accessed through the VRDC by Advarra (Columbia, MD, USA).

PFIZER CONFIDENTIAL

10.2. Patient Consent

As this study involves deidentified/anonymized structured data, which according to applicable legal requirements do not contain data subject to privacy laws, obtaining informed consent from patients by Pfizer is not required.

10.3. Institutional Review Board (IRB)/Ethics Committee (EC)

This study does not require IRB/EC approval. An exemption was received.

10.4. Ethical Conduct of the Study

The study will be conducted in accordance with legal and regulatory requirements, as well as with scientific purpose, value, and rigor and follow generally accepted research practices described in Guidelines for Good Epidemiologic Practice practices laid out in 2005 FDA Good Pharmacoepidemiology Practices (GPP),² Best Practices for Conducting and Reporting Pharmacoepidemiologic Safety Studies Using Electronic Healthcare Data Sets,²² and the 2015 International Society of Pharmacoepidemiology GPP.²³

11. MANAGEMENT AND REPORTING OF ADVERSE EVENTS/ADVERSE REACTIONS

This study involves data that exist as structured data by the time of study start. In these data sources, individual patient data are not retrieved or validated, and it is not possible to link (i.e., identify a potential association between) a particular product and medical event for any individual. Thus, the minimum criteria for reporting an adverse event (AE) (i.e., identifiable patient, identifiable reporter, a suspect product, and event) cannot be met.

12. PLANS FOR DISSEMINATING AND COMMUNICATING STUDY RESULTS

In the event of any prohibition or restriction imposed (e.g., clinical hold) by an applicable competent authority in any area of the world, or if the party responsible for collecting data from the participant is aware of any new information which might influence the evaluation of the benefits and risks of a Pfizer product, Pfizer should be informed immediately.

ANNEX 1. LIST OF STANDALONE DOCUMENTS

None.

ANNEX 2. ADDITIONAL INFORMATION

			Codes
Variable	Role	Data Source(s)	
Elranatamab	Inclusion criteria	Claims data	HCPCS: C9165, J1323 NDC: 00069449401, 00069449402, 00069252201, 00069252202 ICD-10 Procedure code: XW013L9 Generic name: Elranatamab
Teclistamab	Inclusion criteria	Claims data	HCPCS: J9380, C9148 NDC: 57894044901, 57894045001 ICD-10 Procedure code: XW013487Generic name: Teclistamab
Multiple Myeloma	Inclusion criteria, Outcome - HCRU	Claims data	C90.0x
Age	Inclusion criteria, Baseline characteristic - Demographic	Claims data	N/A
Sex	Baseline characteristic - Demographic	Claims data	N/A

Dagg/Etlan! -: t	Baseline	Claims	N/A
Race/Ethnicity	characteristic - Demographic	data data	N/A
US Census Region	Baseline characteristic - Demographic	Claims data	N/A
State	Baseline characteristic - Demographic	Claims data	- N/A
BCMA-directed therapy	Baseline characteristic - Treatments, Outcome - HCRU	Claims data	CPT: 0537T, 0538T, 0539T, 0540T HCPCS: C9081, C9098, Q2055, Q2056, J9037, C9069 NDC: 57894011101, 57894011102, 59572051501, 59572051502, 59572051503, 00173089601 Generic names: Idecabtagene Vicleucel, Ciltacabtagene Autoleucel, Belantamab ICD10PCS: XW033K7, XW043K7, XW043A7, XW043A7, XW033A7
CAR-T	Baseline characteristic - Treatments, Outcome - HCRU	Claims data	CPT: 0537T, 0538T, 0539T, 0540T HCPCS: C9081, C9098, Q2055, Q2056 NDC: 57894011101, 57894011102, 59572051501, 59572051502, 59572051503 Revenue codes: 0871, 0872, 0873, 0874, 0891 ICD10PCS: XW033C7 XW033G7 XW033J7 XW033K7 XW043C7 XW043G7 XW043K7 Generic names: Idecabtagene Vicleucel, Ciltacabtagene Autoleucel
Hematopoietic stem cell transplantation	Baseline characteristic - Treatments	Claims data	CPT: 38240, 38241, 38242, 38243 HCPCS: A52879, S2150 ICD-10 Diagnosis: T86.0, T86.00, T86.01, T86.02, T86.03, T86.09, T86.5, Z48.290, Z94.81, Z94.84 ICD-10 Procedure: 30240Y0, 30243Y0, 30250Y0, 30253Y0, 30260Y0, 30263Y0, 30230Y1, 30233Y1, 30240Y1, 30243Y1, 30230Y2, 30233Y2, 30240Y2, 30243Y2, 30230Y3, 30233Y3, 30240Y3, 30243Y3, 30230Y4, 30233Y4, 30240Y4, 30243Y4, 30253Y1, 30260Y1, 30263Y1, 30233X0,

Talquetamab	Baseline characteristic - Treatments, Outcome - HCRU	Claims data	30233G0, 30233G1, 30233G2, 30233G3, 30233X1, 30233X2, 30233X3, 30233X4, 30233Y0, 30243X0, 30243G0, 30243G1, 30243G2, 30243G3, 30243X1, 30243X2, 30243X3, 30243X4, 0243Y4, 30283X0, 30283G0, 30283G1, 30283G2, 30283G3, 30283X1, 30283X2, 30283X3, 30283Y4, 30283Y1, 30283Y2, 30283Y3, 30283Y4 HCPCS: C9163 NDC: 57894046901, 57894047001 Generic name: Talquetamab
Proteasome inhibitors	Baseline characteristic - Treatments, Outcome - HCRU	Claims data	HCPCS: C9295, J9041, J9044, J9046, J9047, J9048, J9049, S0115 NDC: 00143909801, 00409170001, 00409170301, 00409170401, 00781325870, 10019099101, 25021024410, 43598042660, 43598086560, 50742048401, 51817058601, 55150033701, 60505605004, 63020004901, 63020007801, 63020007802, 63020007901, 63020007902, 63020008001, 63020008002, 63323082110, 68001053436, 68001054036, 68001054136, 70511016105, 70511016202, 70710141101, 70771170801, 70860022510, 71288011810, 72205018301, 72266024301, 76075010301, 83090000801 Generic names: Bortezomib, Carfilzomib, Ixazomib
Immunomodulatory drugs	Baseline characteristic - Treatments, Outcome - HCRU	Claims data	NDC: 00378193501, 00378193528, 00378193601, 00378193628, 00378193701, 00378193728, 378194001, 00378194021,00 00378194101, 00378194121, 00378194201, 00378194221, 00480124128, 00480124228, 00480124328, 00480124421, 00480124521, 00480124621, 31722025701, 31722025728, 31722025801, 31722025828, 31722025901, 31722025928, 31722026001, 31722026021, 31722026101, 31722026121, 31722026201, 31722026221, 43598051101, 43598051163, 43598051201, 43598051201, 43598051521, 43598051301, 43598051501, 43598051521, 43598051601, 43598051663, 47781048401, 47781048401, 47781048528, 47781048401, 4778104877, 47781048801, 47781048877, 59572020594, 59572020597, 59572021015, 59572021095, 59572021513, 59572021593,

			50572022016 50572022006 50572040200
			59572022016, 59572022096, 59572040200, 59572040228, 59572040528, 59572040500, 59572040528, 59572041000, 59572041028, 59572041500, 59572041521, 59572042501, 59572042501, 59572042501, 59572050200, 59572050221, 59572050300, 59572050221, 59572050300, 59572050321, 59572050400, 59572050421, 59651034201, 59651034207, 59651034228, 59651034201, 59651034207, 5965103428, 59651034401, 59651034407, 59651034428, 59651034501, 59651034407, 59651034421, 59651034501, 59651034507, 59651034521, 59651034601, 59651034607, 59651034521, 59651034601, 59651034607, 59651034721, 60505453202, 60505453301, 60505453302, 60505453401, 60505453501, 60505453502, 60505453602, 60505453701, 60505453702, 63304004101, 63304004127, 63304004201, 63304004227, 63304004401, 63304004227, 63304004401, 63304004422, 63304004501, 63304004422, 63304004401, 63304004422, 63304004501, 63304004522, 63304004601, 63304004522, 63304004601, 63304004522, 6300505453501, 70710103001, 70710103007, 70710103101, 70710103101, 70710103107, 70710103201, 70710103207, 70710103301, 70710103308, 70710103207, 70710103408, 70710103501, 70771167801, 70771167801, 70771167801, 70771167801, 70771167801, 70771167801, 70771168008, 70771168101, 70771168008, 70771168101, 70771168008, 70771168101, 70771168008, 70771168001, 70771168008, 70771168101, 70771168008, 70771168101, 70771168008, 70771168101, 70771168008, 70771168101, 70771168008, 70771168101, 70771168008, 70771168101, 70771168008, 70771168001, 70771168008, 70771168101, 70771168008, 70771168001, 70771168008, 70771168101, 70771168008, 70771168001, 70771168008, 70771168101, 70771168008, 70771168001, 70771168008, 70771168001, 70771168008, 70771168001, 70771168008, 70771168001, 70771168008, 70771168001, 70771168008, 70771168001, 70771168008, 70771168001, 70771168008, 70771168001, 70771168008, 70771168001, 70771168008, 70771168001, 70771168008, 70771168001, 70771168008, 70771168001, 70771168008, 70771168001, 70771168008, 70771168001, 70771168008, 70771168001, 70771168001, 70771168008, 70771168001, 70771168001, 70771168001, 70771168001, 7070
Steroids	Baseline	Claims	Pomalidomide HCPCS: C9034, C9256, J1020, J1030, J1040,
2.53.0.445	characteristic - Treatments, Outcome - HCRU	data	J1094, J1095, J1096, J1100, J2920, J2930, J7312, J7509, J7637, J7638, J8540, K0512, K0513, S0173, J7506, J7512 Generic names (and associated NDCs): Dexamethasone, Methylprednisolone,
			Prednisone, Prednisolone
CD38 mAbs	Baseline characteristic - Treatments, Outcome - HCRU	Claims data	HCPCS: C9062, C9476, J9144, J9227, J9145 NDC: 00024065401, 00024065601, 57894050205, 57894050220, 57894050301, 57894050505, 57894050520 Generic names: Daratumumab, Isatuximab
mAbs	Baseline characteristic - Treatments,	Claims data	HCPCS: C9062, C9476, J9144, J9227, J9145, C9477, J9176

	0 :		NDC 00004065401 00004065601
	Outcome - HCRU		NDC: 00024065401, 00024065601, 57894050205, 57894050220, 57894050301, 57894050505, 57894050520, 00003229111, 00003452211
			Generic names: Daratumumab, Isatuximab, Elotuzumab
Chemotherapies	Baseline characteristic - Treatments, Outcome - HCRU	Claims data	HCPCS: C9080, C9087, C9243, C9420, C9421, J8530, J8600, J9033, J9034, J9036, J9056, J9058, J9059, J9070, J9071, J9080, J9090, J9091, J9092, J9093, J9094, J9095, J9096, J9097, J9245, J9246, J9247,
			J9000, C9415, J9002, Q2048, Q2049, Q2050, J9001, J9181, J9182, C9425, J8560, C9414, C9418, J9060, J9062
			Generic names (and associated NDC codes): Melphalan, Bendamustine, Cyclophosphamide, Doxorubicin, Etoposide, Cisplatin
Small molecule inhibitors	Baseline characteristic - Treatments, Outcome - HCRU	Claims data	NDC: 00074056111, 00074056114, 00074056607, 00074056611, 00074057611, 00074057622, 00074057630, 00074057634, 00074057928
	пско		Generic name: Venetoclax
Nuclear export inhibitors	Baseline characteristic - Treatments, Outcome - HCRU	Claims data	NDC: 72237010401, 72237010101, 72237010102, 72237010103, 72237010104, 72237010105, 72237010106, 72237010107, 72237010202, 72237010206, 72237010207, 72237010305
			Generic name: Selinexor
Antivirals	Baseline characteristic - Treatments	Claims data	HCPCS/CPT: J0133, Q4075, S0071, G9017, G9033, S0137, J1324, J1452, J1455, 67027, C9412, J1570, J1574, J7310, J1746, G9019, G9035, J2547, J0248, J0741, G9020, G9036, S0140, 0025U, G9018, G9034, J3485, S0104
			Generic names (and associated NDC codes): Abacavir, Acyclovir, Amantadine, Atazanavir, Baloxavir Marboxil, Bictegravir, Brivudin, Cobicistat, Daclatasvir, Darunavir, Delavirdine, Didanosine, Dolutegravir, Doravirine, Efavirenz, Elvitegravi, Emtricitabine, Enfuvirtide, Entecavir, Etravirine, Fameiclovir, Fomivirsen, Fosamprenavir, Foscarnet, Fostemsavir, Ganciclovir, Ibalizumab, Indinavir, Lamivudine, Ledipasvir, Lenacapavir, Letermovir, Lopinavir, Maraviroc, Maribavir, Molnupiravir, Nelfinavir,

			NT 1 NT 1 NT 1 NT 1 NT 1 NT 1
	D 1	CI.	Nevirapine, Nevirapine, Nirmatrelvir/Ritonavir, Oseltamivir, Pemivibart, Penciclovir, Peramivir, Raltegravir, Remdesivir, Rilpivirine, Rimantadine, Ritonavir, Saquinavir, Simeprevir, Sofosbuvir, Stavudine, Tecovirimat, Tenofovir, Tenofovir, Tipranavi, Valaciclovir, Valacyclovir, Valganciclovir, Vilobelimab, Zanamivir, Zidovudine
Antibiotics	Baseline characteristic - Treatments	Claims data	HCPCS/CPT: 4041F, 4047F, 4048F, C9001, C9039, C9054, C9116, C9124, C9228, C9241, C9258, C9282, C9443, C9444, C9446, C9462, G8152, G8191, G8192, G8195, G8197, G8198, G8199, G8503, G8504, G8527, G8629, G8630, G9315, J0120, J0121, J0122, J0200, J0278, J0290, J0291, J0295, J0456, J0530, J0540, J0550, J0558, J0559, J0560, J0561, J0580, J0689, J0690, J0691, J0692, J0694, J0695, J0696, J0697, J0698, J0699, J0701, J0703, J0710, J0712, J0713, J0714, J0715, J0720, J0742, J0743, J0744, J0770, J0875, J0877, J0878, J1267, J1335, J1362, J1364, J1580, J1590, J1840, J1850, J1890, J1956, J2010, J2020, J2021, J2184, J2185, J2186, J2265, J2280, J2281, J2406, J2407, J2460, J2510, J2540, J2543, J2700, J2770, J2970, J3000, J3090, J3095, J3243, J3244, J3260, J3320, J3370, J3371, J3372, J7342, J7682, J7685, Q0144, S0016, S0021, S0024, S0030, S0032, S0034, S0039, S0040, S0072, S0073, S0074, S0077, S0081, S0085, S0142, S0143, J0457, J0688, J0687, J0736, J0737, J0872, J0873, J0874, J1271, J1836, J2290, J3374, J3375, J2183
			Generic names (and associated NDC codes): Penicillin, Tobramycin, Cycloserine, Vancomycin, Capreomycin, Cefazolin, Streptomycin, Neomycin, Bacitracin, Sulfadiazine, Isoniazid, Cefaclor, Loracarbef, Cefuroxime, Cephalothin, Cefamandole, Ceftazidime, Drotrecogin Alfa, Amoxicillin, Cephradine, Ampicillin, Sulfamethoxazole, Erythromycin, Dicloxacillin, Cloxacillin, Metronidazole, Tetracycline, Doxycycline, Cephalexin, Nitrofurantoin, Aztreonam, Oxacillin, Nafcillin, Cefepime, Sulfisoxazole, Trimethoprim, Sulfisoxazole Acetyl, Ceftriaxone, Erythromycin Ethylsuccinate, Cefixime, Sulfasalazine, Ethambutol, Pyrazinamide, Minocycline, Demeclocycline, Norfloxacin, Cefoxitin, Imipenem, Ertapenem, Ceftizoxime, Cefonicid, Ethionamide,

			Tigecycline, Clindamycin, Lincomycin, Spectinomycin, Gentamicin, Cefpodoxime, Linezolid, Rifabutin, Gatifloxacin, Amikacin, Kanamycin, Cefadroxil, Cephapirin, Sulfanilamide, Sulfacetamide, Chloramphenicol, Dapsone, Polymyxin, Nalidixic Acid, Mafenide, Lomefloxacin, Mezlocillin, Ciprofloxacin, Ciprofloxacin Lactate, Moxifloxacin, Clofazimine, Mupirocin, Ticarcillin, Cefotetan, Cefotaxime, Silver Sulfadiazine, Levofloxacin, Oxytetracycline, Cefoperazone, Trovafloxacin Mesylate, Clarithromycin, Tinidazole, Ofloxacin, Doripenem, Sulfathiazole, Rifampin, Chloramphenicol Sod Succinate, Meropenem, Azithromycin, Cefdinir, Paromomycin, Colistin, Enoxacin, Sparfloxacin, Quinupristin, Netilmicin, Ceftibuten, Cefprozil, Rifapentine, Telithromycin, Daptomycin, Furazolidone, Bismuth Subsalicylate, Grepafloxacin, Piperacillin, Cefditoren, Ceftaroline Fosamil, Fosfomycin Tromethamine, Telavancin, Polymyxin B Sulfate, Gemifloxacin, Rifaximin, Sarecycline, Bacitracin, Chloramphenicol Palmitate, Chlortetracycline, Trimethoprim, Aminosalicylic, Pretomanid, Bacitracin Zinc, Fidaxomicin, Colloidal Bismuth Subcitrate, Omeprazole, Rifamycin, Dalbavancin, Cefiderocol, Bedaquiline, Oritavancin, Ceftolozane, Tedizolid, Plazomicin, Ozenoxacin, Delafloxacin Meglumine, Triamcinolone, Omadacycline, Eravacycline, Lefamulin, Ivermectin, Salicylic Acid
Antifungals	Baseline characteristic - Treatments	Claims data	HCPCS: J0285, J0286, J0287, J0288, J0289, 80285, J3465, J1450, J2248, J1835, J0637, J0348
			Generic name (and associated NDC codes): Amphotericin B, Voriconazole, Natamycin, Fluconazole, Micafungin, Posaconazole, Itraconazole, Caspofungin, Anidulafungin, Isavuconazole, Nystatin
Intravenous	Baseline	Claims	CPT: 90283
immunoglobulin	immunoglobulin characteristic - Treatments	data	HCPCS: C9072, C9130, C9270, G0332, J1459, J1554, J1556, J1557, J1566, J1568, J1572, J1576, J1599, Q4087, Q4088, Q4091, Q4092, Q4097, Q9941, Q9942, Q9943, Q9944
			ICD-10 Procedure: 30233S1, 30243S1, 30253S1, 30263S1
			NDC: 00026064012, 00026064020, 00026064071, 00026064512, 00026064515,

00026064520, 00026064524, 0002606 00026064612, 00026064620, 0002606 00026064625, 00026064671, 0002606	-
	64624. I
00026064625, 00026064671, 0002606	-
	64812,
00026064815, 00026064820, 0002606	64871,
00026064912, 00026064920, 0002606	64924,
00026064971, 00069101101, 0006910	01102,
00069110901, 00069110902, 0006912	22401,
00069122402, 00069131201, 0006913	31202,
00069141501, 00069141502, 0006915	55801,
00069155802, 00078012058, 0007801	12094,
00078012219, 00078012259, 0007801	
00078012419, 00078012460, 0007801	
00078024419, 00078024493, 0019200	-
00192064020, 00192064025, 0019206	-
00192064912, 00192064920, 0019206	-
00192064971, 00944047169, 0094404	-
00944047175, 00944047180, 0094420	-
00944262002, 00944262003, 0094426	,
00944262005, 00944262006, 0094426	-
00944262008, 00944262302, 0094426	-
00944262503, 00944262607, 0094426	,
00944262808, 00944265503, 0094426	-
00944265603, 00944265707, 0094426	-
00944265908, 00944280704, 0527694	
13533064512, 13533064515, 1353306	
13533064512, 13533064513, 1353306	,
13533064620, 13533064624, 1353306	-
13533064620, 13533064624, 1353306	-
13533064671, 13533064812, 1353306	-
	-
44206012058, 44206012259, 4420601	-
44206022600, 44206022601, 4420602	-
44206026763, 44206026866, 4420602	-
44206041501, 44206041603, 4420604	-
44206041706, 44206041791, 4420604	-
44206041892, 44206043605, 4420604	,
44206043710, 44206043791, 4420604	-
44206043892, 44206043940, 4420604 44206043993, 44206050551, 4420605	
	,
44206050756, 44206050806, 4966916	
49669161301, 49669161401, 4966916	
49669162301, 49669162401, 5276902	
52769026972, 52769027071, 5276902	
52769027076, 52769027082, 5276904	,
52769041603, 52769041706, 5276904	-
52769047172, 52769047175, 5276904	
54129023310, 54129023350, 5423802	,
59730650201, 59730650301, 6195300	-
61953000302, 61953000303, 6195300	
61953000400, 61953000401, 6195300	-
61953000403, 61953000404, 6195300	
61953000406, 61953000407, 6195300	-
61953000409, 61953000501, 6195300	-
61953000503, 61953000504, 6195300	
61953000506, 64193025050, 6420819	
64208823401, 64208823402, 6420882	23403,

